4. STUDY DESIGN

4.1. Overview of Study Design

This is a phase 2 study designed to examine the bone anabolic effect of the next generation proteasome inhibitor, ixazomib, in relapsed/refractory myeloma patients. Treatment consists of ixazomib 4 mg on days 1, 8, 15, 22 of a 28-day cycle, for a maximum of 6 cycles).

General eligibility criteria may be assessed prior to the formal Screening period if it is part of standard clinical practice. However, per the Schedule of Events, formal screening will occur during the Screening period, which may last for up to 35 days prior to initiating study treatment. Determination of relapsed/refractory disease as an entry criterion may be based on patient data obtained during or following the patient's most recent prior antineoplastic therapy.

Study drug (ixazomib 4.0 mg) will be given on Days 1, 8, 15, 22 of a 28- day cycle for a maximum of 6 cycles. Dose modifications may be made based on toxicities during treatment. Patients will be discontinued from the study for progressive disease or unacceptable toxicity.

Treatment periods will be defined as 28-day cycles. Patients will be seen once per treatment cycle (Day 1) during their participation in the active treatment of the study. More frequent follow-up would be only as clinically indicated at the discretion of the treating physician.

Patients will be assessed for disease response and progression. Response will be assessed according to the International Myeloma Working Group (IMWG) criteria (see APPENDIX A) for all patients every 4 weeks for a maximum of 6 cycles (unless disease progression or unacceptable toxicity).

ECOG performance score (APPENDIX B), adverse events (AEs), laboratory values, and vital sign measurements will be collected and assessed throughout the study. Toxicity will be evaluated according to National Cancer Institute Common Terminology Criteria for Adverse Events (NCI CTCAE), version 4.03, effective date 14 June 2010.

Patients will attend an End of Treatment (EOT) visit after completion of their 6 cycles (or at study discontinuation due to progressive disease, unacceptable toxicity, or other reason) and will continue to be followed for survival.

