- Meets all of the criteria for Partial Response (PR) and
- Serum and urine M proteins detectable by immunofixation but not on electrophoresis or
- ≥ 90% reduction in serum M protein **and** urine M protein < 100 mg/24 hrs.

Partial Response (PR):

- If the patient had soft tissue plasmacytomas present at baseline and they were assessed at this disease assessment: ≥ 50% reduction in size of soft tissue plasmacytomas (see Appendix A; Notes h.)*and*
- If the patient had ≥ 30% plasma cells in bone marrow at baseline and a bone marrow biopsy was done: ≥ 50% reduction in plasma cells **and**
- ≥ 50% reduction in serum M protein **and** reduction in urine M protein ≥ 90% or to < 200 mg/24hr **or**
- If patient had serum M protein < 1 g/dL, urine M protein < 200 mg/24 hrs, and an involved serum free light chain level ≥ 10 mg/dL at baseline: ≥ 50% decrease in the difference between involved and uninvolved serum free light chain levels

Stable Disease (STA):

• Patient does not meet criteria for Stringent Complete Response, Complete Response, Very Good Partial Response, Partial Response, or Progression.

Progression (PROG): Any one or more of the following:

- Serum M protein increase ≥ 25% from baseline (or an increase of ≥ 1 g/dL if serum M protein was ≥ 5 g/dL at baseline), with an absolute increase of ≥ 0.5 g/dL or
- Urine M protein increase ≥ 25% from baseline, with an absolute increase of ≥ 200 mg/24 hrs or
- If patient had serum M protein < 1 g/dL, urine M protein < 200 mg/24 hrs, and an involved serum free light chain level ≥ 10 mg/dL at baseline: ≥ 25% increase in the difference between involved and uninvolved serum free light chain level, with an absolute increase of ≥ 10 mg/dL or
- Bone marrow plasma cell percentage increase ≥ 25% from baseline, with the absolute plasma cell % ≥ 10% or
- New bone lesions or soft tissue plasmacytomas, or definite increase in size of existing bone lesions or soft tissue plasmacytomas (see Appendix A: Notes h.) or
- Development of hypercalcemia (corrected serum calcium > 11.5 mg/dL or 2.65 mmol/L) that can be attributed solely to multiple myeloma

NOTE: If a disease assessment indicates that a patient is experiencing a Stringent Complete Response, Complete Response, Very Good Partial Response, Partial Response, or Progression, this should be confirmed by a second disease assessment and this should be done prior to the institution of any new therapy. The second disease assessment may be done at any time.

Notes:

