Best Response: This is calculated from a sequence of Objective Status evaluations

Stringent Complete Response (sCR): An objective status of Stringent Complete Response on at least two sequential disease assessments. Only one bone marrow biopsy, done during one of these two disease assessments, is required to confirm the response.

Complete Response (CR): An objective status of Complete Response on at least two sequential disease assessments. Only one bone marrow biopsy, done during one of these two disease assessments, is required to confirm the response.

Very Good Partial Response (VGPR): An objective status of Very Good Partial Response on at least two sequential disease assessments.

Partial Response (PR): An objective status of Partial Response on at least two sequential disease assessments.

Unconfirmed sCR (UsCR): One objective status of Stringent Complete Response (based on evidence from serum and urine studies and, if drawn, bone marrow biopsy) but the confirmation studies are either not done, or when done, do not meet the requirements necessary to confirm response. This must be documented before progression and at least three weeks after registration.

Unconfirmed CR (UCR): One objective status of Complete Response (based on evidence from serum and urine studies and, if drawn, bone marrow biopsy) but the confirmation studies are either not done, or when done, do not meet the requirements necessary to confirm response. This must be documented before progression and at least three weeks after registration.

Unconfirmed VGPR (UVGPR): One objective status of Very Good Partial Response, but the confirmation studies are either not done, or when done, do not meet the requirements necessary to confirm response. This must be documented before progression and at least three weeks after registration.

Unconfirmed PR (UPR): One objective status of Partial Response, but the confirmation studies are either not done, or when done, do not meet the requirements necessary to confirm response. This must be documented before progression and at least three weeks after registration.

Stable / No Response (STA): At least one objective status of Stable at least three weeks after registration, but not qualifying as any of the above. If radiographic studies were performed there should be no known progressive or new bone lesions.

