Increasing Disease (INC): First objective status recorded (other than Unknowns or those before three weeks) of Progression, provided this occurs within eight weeks of registration.

Inadequate Assessment. Response Unknown (NASS): Progression greater than eight weeks after registration and either all objective statuses prior to registration are unknown or the only known objective statuses occurred less than three weeks after registration.

Relapse: In patients with a confirmed response as described above, relapse is defined as the first occurrence of any of the following, reconfirmed by repeat analysis of serum and/or 24-hour urine M protein, done more than 2 weeks apart:

- a. Myeloma protein increase by more than 100% from the lowest level recorded on study, or a rise of 2.0 g/dl (this increase must be to a level > 1.0 g/dL if it is to constitute the sole manifestation of relapse).
- b. Myeloma protein increase above the response criteria for PR (see criteria for Partial Remission).
- c. Reappearance of M-protein in blood or urine not related to immune recovery or recent infection.
- d. Increase in the size and number of lytic bone lesions recognized on radiographs. New skeletal or MRI lesions, preferentially confirmed by fine needle aspirate.
- e. Myeloma related cytogenetic abnormalities.
- f. BM plasmacytosis > 10% or > 5% light chain restricted, non-diploid, plasma cells on clg/DNA.
- g. Hypercalcemia, not explained by any other cause.

Survival Outcomes

Overall Survival: measured as the time from initial registration to death from any cause.

Event-Free Survival: measured as the time from initial registration to progression/relapse of disease or death from any cause

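### Appendix A confirms a best response only when the same category repeats, so a response still deepening when assessment ends can be left unconfirmed

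*Combined protocol and SAP*

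**What the plan says.** Section 4.1 sets the schedule: "Response will be assessed according to the International Myeloma Working Group (IMWG) criteria (see APPENDIX A) for all patients every 4 weeks", up to six cycles. Appendix A then works in two steps. Each assessment receives one objective status. Best Response follows from these: "This is calculated from a sequence of Objective Status evaluations".

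The confirmed levels are defined in parallel. PR is "An objective status of Partial Response on at least two sequential disease assessments". VGPR is "An objective status of Very Good Partial Response on at least two sequential disease assessments". CR is "An objective status of Complete Response on at least two sequential disease assessments", with one marrow biopsy sufficient. Stringent CR (sCR) has the same form. A single status without qualifying confirmation goes to a named unconfirmed category (UsCR, UCR, UVGPR or UPR).

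Two other parts of Appendix A bear on this. The VGPR status definition begins "Meets all of the criteria for Partial Response (PR) and", whereas the CR definition makes no reference to PR or VGPR. The NOTE after the progression criteria asks for confirmation by a second assessment before any new therapy. It lets that assessment fall at any time and does not say which category it must show.

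The relapse definition opens "In patients with a confirmed response as described above, relapse is defined as the first occurrence of" and then lists its triggers, so it covers confirmed responders only.

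**The concern.** A confirmation rule exists to guard against a single spurious reading. PR followed by VGPR is stronger evidence of at least a partial response than one reading alone, yet the literal rule treats the second reading as failing to confirm the first. Without an 'or better' clause, a patient can respond at every visit and hold no confirmed response, while a patient who stays in PR is confirmed.

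Myeloma response is one side of a secondary objective (Section 2.2) and a secondary endpoint (Section 3.2). Section 9.1 does not define the response variable for that association, which leaves Appendix A as the only definition to hand. Two analysts could classify the same patient differently, and the choice could be made after the data are seen.

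Confirmation also decides which patients come under the relapse rule. Some relapse triggers are measured from the lowest on-study level or from reappearance of M-protein, whereas M-protein progression is measured from baseline. A patient left unconfirmed falls outside the relapse triggers.

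**Working it through.** The plan states no figure on this point, so there is nothing to reproduce. The check applies the rules to status sequences.

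**Inputs**
- Confirmation rules, the PR criteria within VGPR, and the unconfirmed categories: Appendix A.
- Post-baseline assessments: Day 1 of Cycles 2 to 6 plus end of study (Section 6.2), so 5 + 1 = 6.
- Convention assumed here: Best Response is the highest confirmed level. If none is confirmed, it is the highest status seen, labelled unconfirmed.

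**Three readings**
- *Literal*: the same status on two consecutive assessments.
- *Nested*: as literal, but PR and VGPR next to each other confirm PR, because VGPR meets the PR criteria.
- *Or better*: two consecutive assessments at that level or higher.

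| Sequence | Literal | Nested | Or better |
|---|---|---|---|
| PR, PR, PR | PR | PR | PR |
| PR, VGPR | UVGPR | PR | PR |
| PR, CR | UCR | UCR | PR |
| VGPR, CR | UCR | UCR | VGPR |
| PR, VGPR, CR | UCR | PR | VGPR |
| PR, PR, VGPR, CR | PR | PR | VGPR |
| VGPR, PR, progression | UVGPR | PR | PR |
| PR, VGPR, CR, CR | CR | CR | CR |

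PR, VGPR, CR receives three different answers. The nested reading rescues PR, VGPR but not PR, CR or VGPR, CR.

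**How many patterns are affected**

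Take the ordered statuses Stable < PR < VGPR < CR and sequences of n assessments that never worsen. Their number is C(n+3, 3). A sequence loses confirmation under the literal rule, relative to 'or better', when it contains at least two responses and no response status repeats. In a non-worsening sequence these must be the final assessments, in rising order. For n of 3 or more there are C(3,2) + C(3,3) = 3 + 1 = 4 such sequences.

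- n = 6: C(9,3) = 84; 4/84 = 4.8%
- n = 4: C(7,3) = 35; 4/35 = 11.4%
- n = 3: C(6,3) = 20; 4/20 = 20%

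For n = 6 the four are: four Stable then PR, VGPR; four Stable then PR, CR; four Stable then VGPR, CR; three Stable then PR, VGPR, CR. On the nested reading, two of the four remain unconfirmed (those ending PR, CR and VGPR, CR).

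These are counts of possible patterns and give no probability for a patient. They leave out sCR and sequences that worsen. They also leave out patients who are confirmed at a lower level than 'or better' would give, such as PR, PR, VGPR, CR.

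**Scale per patient**: with 20 patients, one reclassification moves a proportion with confirmed response by 1/20 = 5 percentage points.

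**The case against.** The strongest reply is that the text already permits a sensible reading. VGPR contains the PR criteria, so PR then VGPR meets them twice, and the NOTE asks that a response be confirmed without requiring the identical label. This stands in part: on that reading PR, VGPR, CR is a confirmed PR. But the Best Response lines count statuses rather than criteria met, and nothing comparable links CR to the lower levels. The text is ambiguous for PR, VGPR and still unhelpful for PR, CR and VGPR, CR.

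Second, the NOTE allows a confirming assessment at any time. This stands. A reader might infer that a response improving at the exit visit has no further opportunity to be confirmed. The documents do not support that, because a repeat assessment before new therapy can supply the second reading if it shows the same status.

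Third, a reader might infer that a deepening patient ranks below one who stays in PR, or counts as a non-responder. No ranking of categories is written. UCR is a named category, separate from Stable / No Response, which takes only patients who qualify for nothing above it.

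Fourth, a reader might infer that the rule removes the quickest and deepest responders. It does not: PR, VGPR, CR, CR is a confirmed CR. The loss arises only when assessment ends, or status worsens, before any status repeats.

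Finally, no confirmed response rate, relapse endpoint or event-free survival endpoint appears in Section 3, and Section 9.1 does not say that the association uses confirmed response. This also stands and limits the consequence. It is also why Section 9 should say how the categories are used.

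**Conclusion.** The point holds in a limited form. The wording requires the same category on two sequential assessments. Read literally, it leaves some patients with consecutive responses unconfirmed and records others at a lower level than they twice reached or exceeded. The PR criteria within VGPR resolve this only partly.

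The reach is small: 4 of 84 non-worsening patterns with six assessments, rising to 4 of 20 with three, which is where early stopping for progression or toxicity matters. The number of patients affected cannot be derived from the documents. If there were 4 to 8 responders among the 20 (an assumption; the plan gives no expected response rate), one reclassified patient would be 1/8 to 1/4 of that group, or 12.5% to 25%.

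The rule bears on the secondary response association and on who enters the relapse definition, which in turn feeds the event-free survival definition in Appendix A. The primary endpoint is unaffected. The correction is worth making before response data are analysed, but the study's main conclusion does not depend on it.

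**What to change.** In Appendix A, Best Response, define:
- confirmed PR as PR or better on at least two sequential assessments;
- confirmed VGPR as VGPR or better on at least two sequential assessments;
- confirmed CR as CR or sCR on at least two sequential assessments;
- Best Response as the highest level so confirmed.

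The sCR line can stay as it is, since no higher level exists. In Section 9.1, state how the unconfirmed categories (UsCR, UCR, UVGPR, UPR) enter the association between bone changes and response: grouped with responders, kept separate, or grouped with stable disease.

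The cost is a few lines of text. No extra visits, samples or data are needed, and the statuses already collected are enough to apply the revised rule.

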APPENDIX B

Eastern Cooperative Oncology Group (ECOG) Scale for Performance Status

Grade	Description	
0	Normal activity. Fully active, able to carry on all predisease performance without restriction	
1	Symptoms but ambulatory. Restricted in physically strenuous activity, but ambulatory and able to carry out work of a light or sedentary nature (eg, light housework, office work)	
2	In bed < 50% of the time. Ambulatory and capable of all self-care, but unable to carry out any work activities. Up and about more than 50% of waking hours.	
3	In bed > 50% of the time. Capable of only limited self-care, confined to bed or chair more than 50% of waking hours.	
4	100% bedridden. Completely disabled. Cannot carry on any self-care. Totally confined to bed or chair	
5	Dead	
Source: Oken MM, Creech RH, Tormey DC, Horton J, Davis TE, McFadden ET et al. Toxicity and response criteria of the Eastern Cooperative Oncology Group. Am J		

Clin Oncol 1982; 5 (6):649-55.

APPENDIX C

Diagnostic and Staging Criteria

Diagnostic Criteria

Revised IMWG Diagnostic Criteria for Multiple Myeloma (Rajkumar, et al. 2014) Clonal bone marrow plasma cells ≥ 10% or biopsy-proven bony or extramedullary plasmacytoma^a And any one or more of the following myeloma defining events: Evidence of end organ damage that can be attributed to the underlying plasma cell proliferative disorder, specifically: Hypercalcemia: serum calcium >0.25 mmol/L (>1 mg/dL) higher than the ULN or 0 >2.75 mmol/L (>11 mg/dL) Renal insufficiency: CrCl <40 mL per min^b or SCr >177 µmol/L (>2 mg/dL) 0 Anemia: Hb >20 g/L below the LLN, or Hb <100 g/L 0 Bone lesions: one or more osteolytic lesions on skeletal radiography, CT, or PET-CT^c 0 Any one or more of the following biomarkers of malignancy: ○ Clonal bone marrow plasma cell percentage^a ≥60% Involved:uninvolved serum FLC ratio^d ≥100 0 >1 focal lesions on MRI studies^e 0 CrCl, Creatinine clearance; CT, computed tomography; FLC, free light chain; Hb, hemoglobin; Ig, immunoglobulin; IMWG, International Myeloma Working Group; LLN, lower limit of normal; M protein, monoclonal protein; MRI, magnetic resonance imaging; PET-CT, Positron emission tomography-computed tomography; ULN, upper limit of

^aClonality should be established by showing κ/λ –light-chain restriction on flow cytometry, immunohistochemistry, or immunofluorescence. Bone marrow plasma cell percentage should preferably be estimated from a core biopsy specimen; in case of a disparity between the aspirate and core biopsy, the highest value should be used. ^bMeasured or estimated by validated equations.

^cIf bone marrow has less than 10% clonal plasma cells, more than one bone lesion is required to distinguish from solitary plasmacytoma with minimal marrow involvement.

^dThese values are based on the serum Freelite assay (The Binding Site Group, Birmingham, UK). The involved free light chain must be ≥100 mg/L.

eEach focal lesion must be 5 mm or more in size.

Staging Criteria

International Staging system [ISS]

normal; SCr, serum creatinine

New International Staging System (Greipp, et al, JCO 2005)			
Stage	Criteria	Median Survival (months)	
I	Serum β2-microglobulin < 3.5mg/L Serum Albumin > 3.5 g/dL	62	
II	Not stage I or III	44	
111	Serum β2-microglobulin > 5.5 mg/L	29	
*There are two categories for stage II: serum β 2-microglobulin < 3.5 mg/L but serum albumin < 3.5 g/dL; or serum β 2-microglobulin 3.5 to < 5.5 mg/L irrespective of the serum albumin level.
